9.7.3 Pathologic Complete Response Rate

This is defined as the extent of residual carcinoma assessed semiquantitatively by estimating the proportion of residual cancer cells as a percentage in relation to the total tumor area. The tumor area includes areas of chemotherapy-related tissue injury, tumor necrosis, and fibro-collagenous proliferation. Patients with a complete pathologic response would have no residual cancer cells

would be given 0%, while patients with no response would be given 100%. In patients with multiple tumor nodules, the mean of the values for the various tumor nodules should be reported.

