2.2 Secondary Objectives

- Compare 3- year recurrence-free survival (RFS) between the experimental and control treatment groups.
- Compare 3-year OS between the experimental and control groups
- Compare OS (in both the experimental and control groups) to historical controls
- Evaluate the best overall response rates (both by RECIST 1.1 and surgical pathology) between the experimental and control groups.

- Compare the pathologic complete response rate to neoadjuvant therapy in resected tumor tissue between the experimental and control groups.
- In patients who experience a recurrence after surgery, evaluate the proportion of patients amenable to complete re-resection/ablation between the experimental and control treatment groups.
- In patients who experience a recurrence after protocol therapy, compare the progression free survival post-recurrence between the experimental and control groups.
- Evaluate the perioperative surgical outcomes (complications and severity scores) between the experimental and control groups.
- Compare 3-year OS from the date of registration between experimental and control groups

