4.1 Randomization

1:1 randomization with no stratification.

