5.1.2 Neoadjuvant Therapy

Patients who are eligible for and consent to enroll onto this trial will be randomized to either the control arm or the experimental arm. One cycle is 2 weeks.

- Patients in the control arm (Arm A) will receive mFOLFOX6 and Nivolumab given on Day 1 of every 2 week cycle for 4 cycles (Cycle 1 - Cycle 4). The treatment order for Arm A is Nivolumab followed by mFOLFOX6.
- The experimental arm (Arm B) will receive two doses of Nivolumab and MVA-CV301 each given Days -28, -14, followed by four cycles of Nivolumab plus FPV-CV301 given on Day 1 of every 2 week cycle concurrently with mFOLFOX6, which will again be administered every 2 weeks for 4 cycles (Cycle 1 – Cycle 4). For Arm B the order of administration is Nivolumab followed by the vaccination at least one hour prior to mFOLFOX6.

A window of +2 days between administration of Nivolumab +/- vaccination and mFOLFOX6 is allowed. This window will accommodate subjects that receive their chemotherapy locally. If there is more than a 2-day delay for any reason, administration of study drugs should be re-aligned so that the chemotherapy falls within +2 days with the next cycle.

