8.4 Confidentiality of Biospecimens

Samples that are collected will be identified by a subject's sequence ID assigned at the time of registration to the trial. Any material issued to collaborating researchers will be anonymized and only identified by the subject's study number.

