9.7.2 Objective Response Rate

The objective response rate is the proportion of all subjects with confirmed PR or CR according to RECIST 1.1 and surgical pathology defined as the percent tumor viability (see 9.7.3 for definition), from the start of treatment until disease recurrence.

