12.2.2 Definition of Secondary Objectives and Endpoints

Recurrence-free survival, best overall response rate by RECIST 1.1 and surgical pathology criteria, proportion of patients amenable to complete resection/ablation upon first recurrence, incidence and severity of perioperative surgical complications as described above. In addition, a comparison of 3-year OS between the two groups as well as a comparison of OS in both groups to historical controls.

Secondary Endpoints: include 3-year recurrence-free survival, best overall response rate by RECIST 1.1 criteria and tumor pathology, perioperative complications and the proportion of patients able to undergo resection/ablation of first recurrences.

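### Percent residual tumour, a visual estimate behind two secondary endpoints, can be scored by a pathologist who knows the arm, because nothing in the plan withholds it

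*Combined protocol and SAP*

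**What the plan says.** Section 9.7.3 describes the measure: "This is defined as the extent of residual carcinoma assessed semiquantitatively by estimating the proportion of residual cancer cells as a percentage" of a tumour area that also takes in treatment damage, necrosis and fibrosis. The scale runs from 0% (complete response) to 100% (no response). For several nodules, "In patients with multiple tumor nodules, the mean of the values for the various tumor nodules should be reported". The section does not say who reads the slides, whether the read is local or central, or what the reader knows about treatment.

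The score is used twice:

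- Section 2.2 has the objective "Compare the pathologic complete response rate to neoadjuvant therapy in resected tumor tissue between the experimental and control groups".
- Section 9.7.2 brings in "surgical pathology defined as the percent tumor viability" as part of objective response, and Section 12.2.2 lists "best overall response rate by RECIST 1.1 criteria and tumor pathology" among the secondary endpoints.

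On allocation, Section 4.1 says only "1:1 randomization with no stratification". On treatment before surgery, Section 5.1.2 says "The experimental arm (Arm B) will receive two doses of Nivolumab and MVA-CV301 each given Days -28, -14", followed by vaccine with each of four chemotherapy cycles. Arm A receives no vaccine and no placebo.

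On specimens, Section 8.4 labels collected samples with a sequence ID given at registration and adds: "Any material issued to collaborating researchers will be anonymized and only identified by the subject's study number". Section 8.1.2 leaves tissue handling to each site's own procedures.

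**The concern.** A percentage estimated by eye leaves room for judgement: where the tumour area ends, how much viable tumour remains in it, and how to weigh mixed fields. A reader who knows that a specimen comes from the vaccine arm can lean towards the expected result without intending to. Randomisation does not protect against this, because the error enters when the outcome is measured.

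Two between-arm comparisons would be affected. Both bear on whether vaccination before surgery acts on the tumour, and they would be read early, long before 3-year survival is known. Once specimens have been scored with arm known, masking can be recovered only by reading them again.

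**Working it through.** The plan gives no expected response rate, standard deviation, significance level or power for pathologic response, so there is no planned figure for this endpoint to reproduce. The check is mainly a reading of the text, followed by an illustration of scale.

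**Step 1: does anything mask the reader?**

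| Section | What it covers | Does it withhold arm from the scorer? |
|---|---|---|
| 4.1 | 1:1 allocation, no strata | No; masking is not mentioned |
| 5.1.2 | Vaccine in Arm B only, no placebo | No; the arms visibly differ |
| 8.1.2 | Tissue handled under site procedures | No |
| 8.4 | Sequence ID; anonymised material for researchers | No; identity only |
| 9.7.3 | How the score is made | No; the reader is not described |
| 14.4 | General confidentiality | No |

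Before surgery Arm B has 2 + 4 = 6 vaccine dosing days, and Arm A has none.

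**Step 2: how many patients carry the comparison?** Section 12.3 plans 70 resected patients, 35 per arm. This agrees with its enrolment of 74 and 5% unresected: 74 × 0.95 = 70.3. One patient is 1/35 = 2.9 points of a response rate, two are 2/35 = 5.7 points, and three are 3/35 = 8.6 points.

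**Step 3: illustration for the graded score.** Assumptions, none from the documents: no true difference, a two-sided 5% test, and a uniform shift in Arm B readings. The standard error is SD × √(2/35) = SD × 0.239, which is 5.98, 7.17 or 8.37 points for an SD of 25, 30 or 35. The rejection rate is 1 − Φ(1.96 − shift/SE) + Φ(−1.96 − shift/SE).

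| Shift in Arm B | SD 25 | SD 30 | SD 35 |
|---|---|---|---|
| 0 points | 5.0% | 5.0% | 5.0% |
| 5 points | 13.3% | 10.7% | 9.2% |
| 10 points | 38.7% | 28.6% | 22.3% |

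**Step 4: illustration for the 0% call.** A fraction u of Arm B non-complete specimens is called complete, so the Arm B rate becomes p + (1 − p)u. For p = 10% and u = 5% this is 0.10 + 0.90 × 0.05 = 14.5%. The rates below come from exact enumeration of the pooled two-proportion test at 35 per arm, two-sided 5%.

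| u | True rate 5% | 10% | 20% |
|---|---|---|---|
| 0 | 3.6% | 5.7% | 4.9% |
| 5% | 12.0% | 9.5% | 6.6% |
| 10% | 28.8% | 19.1% | 11.7% |

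These tables show what an arm-dependent error of a given size would do. They are not evidence that such an error will occur.

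**Step 5: a handful of miscalls on the 0% call.** With a true rate of 10% (3.5 of 35 expected), two extra calls in Arm B give 5.5/35 = 15.7%. The pooled rate is 12.9%, SE = √(0.129 × 0.871 × 2/35) = 0.080, z = 0.057/0.080 = 0.71 and p ≈ 0.48. Three extra calls give 6.5/35 = 18.6%, z = 1.02 and p ≈ 0.31. Neither result is close to significant.

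**The case against.** The strongest reply is that the gap is silence and not a demonstrated fault. No section says what the pathologist is told. The extra Arm B visits are seen by patients and treating staff, not by someone looking at slides. Specimen procedures are partly deferred to a correlative laboratory manual that is not in the documents. Section 8.4 is also wider than its rule on collaborating researchers, since all collected samples carry a sequence ID. The complete-response call has a hard criterion, no residual cancer cells, and because a mean of non-negative scores is zero only when every one is zero, it must hold in every nodule. Pathologic complete response is one of nine secondary objectives, and Section 12.2.2 does not list it separately.

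Much of this stands, and it limits the point. A reader might infer more than the documents support:

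- That the trial is stated to be open-label. The available text uses that term only for another CV301 trial (Section 1.3.3). Here it is inferred from the lack of placebo or masking.
- That the pathologist will know the arm, for instance from the request form. No section describes that form; the plan only fails to prevent it.
- That this is the main early read-out with nothing objective behind it. RECIST response is also assessed before surgery, and the 0% call has a stated criterion.
- That a few miscalls on the 0% call would produce a false claim. Step 5 shows that two or three would not.

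The reply does not supply a mask. A sequence ID hides who the patient is, not which arm the patient is in, and Section 9.7.3 does not refer to the laboratory manual.

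**Conclusion.** The point holds as a cheap improvement. Followed as written, the plan allows a reader who knows the arm to score a judgement-based measure used in two between-arm secondary comparisons. The graded percentage is the more exposed of the two uses, because it leaves the reader more discretion than the 0% call. Overall survival, defined by death from any cause, is not affected, and neither sample size nor significance level changes.

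The size of any bias cannot be derived from the documents. The error rates above rest on assumed SDs, assumed true response rates and an assumed reading error in one direction only. The conclusion also rests on the available text being complete on masking. If the laboratory manual or another study document already withholds arm from the scorer, a cross-reference in Section 9.7.3 would settle the matter.

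**What to change.** Add to Section 9.7.3: *The pathologist reading the resection specimen records percent residual tumour for each nodule on the study form before arm or vaccine exposure is disclosed. Arm is available at any time on clinical request. The form notes whether arm was known when the score was made.*

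The same pathologist reads the same slides, so no extra reader or procedure is needed. The note on the form allows the comparison to be repeated in the reads made without knowledge of arm.

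The cost is low but not nil. Site paperwork changes slightly at each centre, and some reads will be unmasked where arm is needed for diagnosis.

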9.7.4 Recurrence Free Survival

A measurement from the date of recurrence after metastasectomy by RECIST 1.1 or death occurs. Subjects who have not progressed will be right-censored at the date of the last disease evaluation.

9.7.5 Perioperative Surgical Outcomes

Complications and their severities using the Clavien-Dindo classification for severity scores should be recorded.

10 DRUG INFORMATION

CV301 is the investigational agent involved in this study. mFOLFOX6 is an FDA approved regimen. Nivolumab is a human programmed death receptor-1 (PD-1) blocking antibody approved by the FDA at the dose of 240 mg every 2 weeks, and 480 mg every 4 weeks.

10.1 CV301

Please refer to the current version of the Investigator's Brochure (IB) for additional information regarding this vaccine.

CV301 is comprised of two recombinant poxviral vectors to be used together in a prime-boost vaccination regimen. The priming vector is a highly attenuated, non-replicating vaccinia virus Modified Vaccinia Ankara-Bavarian Nordic-CV301 (MVA-BN-CV301) and the boost is a recombinant fowlpox virus (FPV-CV301). Collectively, the regimen is referred to as CV301. CV301 has been designed to consist of five human transgenes to elicit a specific and robust immune response to a variety of cancers. Both viral vectors for CV301 co-express two human tumor-associated antigens (TAA): carcinoembryonic antigen (CEA) and mucin-1 (MUC-1), and three human costimulatory molecules: B7.1, intercellular adhesion molecule-1 (ICAM-1), and leukocyte function-associated antigen-3 (LFA-3) (or TRIad of COstimulatory Molecules, TRICOM™). The three costimulatory molecules are included to maximize the immune response to the TAAs. The anti-tumor mechanism of action for CV301 poxvirus-based immunotherapy is to induce the generation of tumor antigen-specific killer T cells capable of infiltrating the tumor. This tumor-specific T cell immune response is aimed to target and kill antigen-expressing tumor cells throughout the patient's body.

CV301 is a next-generation product based on the prior PANVAC recombinant vector-based therapeutic cancer vaccine, designed to induce an enhanced immune response against the CEA and MUC-1 antigens expressed by many carcinomas. Similarly, to CV301, the previous PANVAC regimen was comprised of two components: a vaccinia vector (PANVAC-V, inalimarev) and a fowlpox vector (PANVAC-F, falimarev), which were investigated for the treatment of a variety of carcinomas including breast, ovarian, colorectal, pancreatic and bladder carcinomas.

10.1.1 Supplier/How Supplied

Bavarian Nordic will supply CV301 at no charge to subjects participating in this clinical trial. MVA-BN-CV301 and FPV-CV301 are each supplied in 2 mL type I borosilicate glass vials closed with sterile bromobutyl rubber stoppers, crimped with aluminum caps and covered with polypropylene closures.

Supplies of both the MVA-BN-CV301 and the FPV-CV301 vaccines will be shipped temperature controlled and monitored to the clinical trial site. Both the MVA-BN-CV301 and the FPV-CV301 vaccines are stored -80°C at the drug depot, and shipped to and stored at the site at -80°C.

The investigator shall take responsibility for and shall take all steps to maintain appropriate records and ensure appropriate supply, storage, handling, distribution, and usage of investigational product in accordance with the protocol and any applicable laws and regulations.

10.1.2 Storage, Preparation and Administration

MVA-BN-CV301 is a liquid-frozen, highly attenuated, live recombinant virus based on the viral vector MVA-BN. Packaging and vials will be labeled according to the respective product specifications.

FPV-CV301 is a liquid-frozen, highly attenuated, live recombinant virus. It is administered as subcutaneous application. The packages and vials will be labeled according to the respective product specifications.

Both the MVA-BN-CV301 and the FPV-CV301 vaccines must be stored at a temperature of -80°C ± 10°C or -20°C ± 5°C; in all cases avoiding direct exposure to light. A vial must not be re-frozen once it has been thawed. Once vaccines are stored at -20°C ± 5°C; storage at -20°C ± 5°C limits the vaccines' use to only 12 months starting with the date of the delivery. Please note that any vaccine stored at -20°C ± 5°C should not be switched to -80°C ± 10°C. It should remain in its current temperature and discarded after 12 months from the date of the delivery.

MVA-BN-CV301 and FPV-CV301 are administered via subcutaneous injection.

Used and unused vials need to be retained in a place with limited access until appropriate drug accountability has been performed. Drug accountability must be documented whenever the vaccine is either prepared or administered. After drug accountability has been performed, used and unused vials should either be returned to BN, to the designated drug depot, or discarded according to local regulations. Destruction or return of vaccine must be agreed upon with BN and appropriately documented. CV301 (MVA-BN-CV301 and FPV-CV301) is categorized as a biological safety level (BSL) 1 genetically modified organism. Therefore, CV301 and any materials that have been in contact with the product should be disposed of according to the respective institutional standards, local and occupational safety guidelines.

Detailed trial-specific instructions on the preparation and administration of MVA-BN-CV301 and FPV-CV301 are provided in a separate Pharmacy Manual supplied to each clinical trial site.

10.2 mFOLFOX

mFOLFOX6 is one of several chemotherapy regimens that include leucovorin calcium (calcium folinate), 5-fluorouracil and oxaliplatin, and which may be used in the treatment of advanced-stage and metastatic colorectal cancer.

For more information on these agents, refer to the FDA approved package inserts. These medications are commercially available.

10.2.1 Oxaliplatin

Oxaliplatin is a platinum alkylating agent, which contains platinum complexed to oxalate and diaminocyclohexane (DACH) complex. Platinum complexes are formed intracellularly and inhibit DNA synthesis through covalent binding of DNA molecules to form intrastrand and interstrand DNA cross-links. Oxaliplatin differs molecularly, from other platinums (cisplatin and carboplatin), by its bulky DACH carrier ligand that most likely accounts for both its efficacy and lack of cross-resistance with other platinum compounds. Cytotoxicity is cell-cycle nonspecific. Oxaliplatin is a radiosensitizing agent.

*Oxaliplatin is incompatible with 0.9% NaCl.

*Oxaliplatin is incompatible in solution with alkaline medications or media and must not be mixed with these.

*Storage and handling materials containing aluminum parts that may come in contact with oxaliplatin should not be used for preparation or mixing of the drug, as aluminum can degrade platinum compounds.

- 1) The lyophilized powder is reconstituted by adding 10 mL (for the 50 mg vial) or 20 mL (for the 100 mg vial) of Water for Injection, USP or 5% Dextrose Injection, USP. Do not administer the reconstituted solution without further dilution.
- 2) After reconstitution in the original vial, the solution may be stored up to 24 hours under refrigeration [2° to 8°C (36° to 46° F)]. Do not freeze the concentrated solution.
- 3) The solution must be further diluted in an infusion solution of 250-500 mL of D5W. A final dilution must never be performed with a sodium chloride solution or other chloride-containing solutions. Concentration must be between 0.2 to 0.7 mg/mL.
- 4) After final dilution with D5W, the shelf life is 6 hours at room temperature [20° to 25°C (68° to 77°F)] or up to 24 hours under refrigeration [2° to 8°C (36° to 46°F)].
- 5) Store under normal lighting conditions at 20°-25°C (68°-77°F); excursions permitted to 15-30°C (59- 86°F). Do not freeze.

10.2.2 Leucovorin

Leucovorin calcium (folic acid) is a reduced form of folic acid. It is usually used 24 hours after methotrexate to selectively “rescue” normal cells from the adverse effects of methotrexate caused by inhibition of production of reduced folates. It is not used simultaneously with

methotrexate, as it might then nullify the therapeutic effect of the methotrexate. Leucovorin has also been used to enhance the activity of fluorouracil by binding to the enzyme thymidylate synthetase and decreasing intracellular levels of thymidylate. Leucovorin is available in D and L stereoisomers; the L stereoisomer is the active moiety.

* Each 50, 100, and 200 mg vial of Leucovorin when reconstituted with 5, 10, and 20 mL, respectively, of sterile diluent yields a leucovorin concentration of 10 mg per mL. Each 350 mg vial of Leucovorin when reconstituted with 17.5 mL of sterile diluent yields a leucovorin concentration of 20 mg per mL. *Leucovorin should not be mixed in the same infusion as fluorouracil as a precipitate may form.

- 1) Reconstitute the lyophilized vial products with Bacteriostatic Water for Injection, USP (benzyl alcohol preserved), or Sterile Water for Injection, USP. When reconstituted with Bacteriostatic Water for Injection, the resulting solution must be used within 7 days. If the product is reconstituted with Sterile Water for Injection, use immediately and discard any unused portion. Because of the benzyl alcohol contained in Bacteriostatic Water for Injection, when doses greater than 10 mg/m² are administered, Leucovorin should be reconstituted with Sterile Water for Injection, and used immediately.
- 2) Dilute leucovorin in 50-1000 mL D5W or NS for infusion. Leucovorin may be mixed in 50mL NS or D5W minibag (doses up to 500mg) or 100mL minibag (doses >500mg) or in 100mL fluid in graduated administration set (D5W, NS or 2/3-1/3). Parenteral admixture is stable for 24 hours stored at room temperature (25°C) and for 4 days when stored under refrigeration (4°C).
- 3) Lyophilized powder vials should be stored at 20° to 25°C (68° to 77° F). Solution for injection should be stored in refrigerator 2° to 8°C (36° to 46°F). Protect from light. Retain in carton until time of use.

10.2.3 Fluorouracil

Fluorouracil was developed based on the observation that tumor cells utilized the base pair uracil for DNA synthesis more efficiently than did normal cells of the intestinal mucosa. It is a fluorinated pyrimidine antimetabolite that is metabolized intracellularly to its active form, fluorouridine monophosphate (FdUMP). The active form inhibits DNA synthesis by inhibiting thymidylate synthetase and the normal production of thymidine. Effects on RNA (incorporation into RNA and RNA inhibition) occur especially with bolus administration. Fluorouracil is cell cycle phase-specific (S-phase).

*1 vial of Fluorouracil Injection contains: 500 mg fluorouracil in 10 ml solution (50 mg/ml); 1000 mg fluorouracil in 20 ml solution (50 mg/ml); 2500 mg fluorouracil in 50 ml solution (50 mg/ml); 5000 mg fluorouracil in 100 ml solution (50 mg/ml)

- 1) Fluorouracil may be mixed in a 50 mL minibag of NS or D5W, yielding a clear, colorless to light yellow solution. Solutions of fluorouracil are expected to be stable in solution 7 days at 37 °C, several weeks at 25 °C, and at least 4 months at 0-4 °C.
- 2) Store 5-fluorouracil in airtight containers protected from light.

